6.3. Other Endpoints

Not applicable.

6.4. Covariates

As for the safety and effectiveness of Anametro, there are no covariates identified from clinical study data thus far obtained or potential covariates.

7. HANDLING OF MISSING DATA

When the seriousness/outcome of adverse events and action taken with Anametro for the adverse events are missing, these data are handled as “unknown” for counting.

8. STATISTICAL METHODS AND STATISTICAL ANALYSIS

8.1. Statistical Methods

8.1.1. Analysis of Continuous Data

Summary statistics (number of patients, mean, standard deviation, median, maximum, and minimum) will be calculated.

8.1.2. Analysis of Categorical Data

The number of patients and proportion of each category will be calculated.

8.1.3. Analysis of Binary Data

The number of patients and proportion will be calculated. If the confidence interval of proportion is calculated, two-sided 95% confidence interval (exact method) will be calculated.

If the proportion is compared between subgroups, risk ratio and its 95% confidence interval, and risk difference and its 95% confidence interval will be calculated. In addition, risk ratio and its 95% confidence interval will be graphically presented (see Appendix 1).

8.2. Statistical Analysis

8.2.1. Overview of Patients

- Number of sites by establisher and number of patients**

In completed patients, the number and proportion of sites by establisher shown below and the number and proportion of patients will be calculated.

- University hospitals
- National hospitals established by the Ministry of Health, Labour and Welfare
- Prefectural and municipal hospitals
- Public organizations
- Hospitals other than the above four established by corporations and individuals
- General practitioners/clinics

In addition, the mean, minimum, and maximum will be calculated for the number of patients per site.

- Dispositions of patients**

In patients who registered to the Study, the number of registered patients, the number of completed patients, the number of patients included in the analysis of safety, the number of patients included in the analysis of clinical response, and the number of patients included in the analysis of microbiological response will be tabulated. In addition, the number of no-CRF-collected patients, the number of patients excluded from the analysis of safety, clinical response, and microbiological response and the number of patients by reason for exclusion will be tabulated.

- Listing of discontinuations and dropouts**

In the safety analysis set, clinical response analysis set, and microbiological response analysis set, the number and proportion of discontinued patients per discontinuation time [<3

days, ≥ 4 to ≤ 7 days, ≥ 8 to ≤ 14 days, ≥ 15 to ≤ 21 days, ≥ 22 days] will be tabulated. In addition, the number and proportion of patients by reason for discontinuation will be tabulated.

- **Listing of excluded patients**

The listing of reasons for exclusion in patients excluded from the analysis of safety and clinical response will be prepared.

8.2.2. Patient Background and Treatment History of Anametro

- **Patient background**

In the safety analysis set, clinical response analysis set, and microbiological response analysis set, the following patient background factors will be tabulated in accordance with Section 8.1.

- Sex [male, female]
- Age (continuous)
- Age group [<15 years, ≥ 15 to <65 years, ≥ 65 years]
- Age group [≥ 10 to <20 years, ≥ 20 to <40 years, ≥ 40 to <65 years, ≥ 65 to <70 years, ≥ 70 to <75 years, ≥ 75 years]
- Inpatient/outpatient status at the first prescription [inpatient, outpatient]
- Body weight (continuous)
- Body Mass Index (continuous)
- Diagnostic name* (anaerobic infection, infectious enterocolitis, amebic dysentery, others)
- Detailed diagnosis name of anaerobic infection
- Severity [mild, moderate, severe, unknown]
- Hepatic dysfunction [absent, present]
- Renal dysfunction [absent, present]
- Past medical history other than hepatic/renal dysfunction [absent, present]
- Concurrent illness other than hepatic/renal dysfunction [absent, present]
- Prior treatment (medication for infection) [absent, present]
- Concomitant medication (medication for infection) [absent, present]

* The same patient may have multiple diagnoses. In such case, additional categories may be added (e.g., anaerobic infection plus infectious enterocolitis).

In addition, patient background will also be tabulated by maximum number of daily doses and by the presence or absence of a central nervous system disorder.

In the safety analysis set, the number and proportion of the following patients will be tabulated by SOCs and PTs of MedDRA.

- Past medical history other than hepatic/renal dysfunction

- Concurrent illness other than hepatic/renal dysfunction.

In the safety analysis set and clinical response analysis set, the number and proportion of the following patients will be tabulated.

- Presence or absence of pregnancy
- Concomitant medication (medication for infection)
- Prior treatment (medication for infection)

- **Status of treatment of Anaemetro**

In the safety analysis set, the following status of treatment of Anaemetro will be tabulated:

- Duration of treatment (continuous)
- Duration of treatment (1) [1, 2, 3, 4, 5, 6, 7, 8, 9, 10, 11, 12, 13, 14, 15, 16, 17, 18, 19, 20, 21, ≥ 22 days]
- Duration of treatment (2) [≤ 3 day, ≥ 4 to ≤ 7 days, ≥ 8 to ≤ 14 days, ≥ 15 to ≤ 21 days, ≥ 22 days]
- Duration of treatment (3) [≤ 3 days, ≥ 4 to ≤ 10 days, > 10 days]
- Maximum dose per single dose [< 500 mg, 500 mg, > 500 mg]
- Mean dose per single dose [< 500 mg, 500 mg, > 500 mg]
- Mean dose per single dose (continuous)
- Maximum number of daily doses [1, 2, 3, 4, > 4 times]
- Mean number of daily doses [< 1 time, 1 time, > 1 to < 2 times, 2 times, > 2 to < 3 times, 3 times, > 3 to < 4 times, 4 times, > 4 times]
- Mean number of daily doses (continuous)
- Dose escalation [absent, present]
- Overdose [absent, present].

The duration of treatment is from the initial day of administration in this Study to the last confirmed day of administration, and is the actual dosing days that excludes the period during which Anaemetro is suspended.

8.2.3. Safety Analysis

Safety analysis will be primarily based on the data collected during the observation period that is from the start of Anaemetro administration to the end of Anaemetro administration.

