7.2.6. Observation period

The observation period shall start on the day the treatment with this drug begins and end on the day the treatment is completed; however, it shall be cut off at Week 8 after the initiation of treatment (Day 56 counting from Day 1 as the day the treatment begins) if the treatment is prolonged.

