7.3.6. Effectiveness evaluation

(1) Clinical response

The clinical response of this drug should be evaluated comprehensively at the completion of the observation period, and the results should be recorded.

If this drug is administered continuously for more than 8 weeks, the clinical response should be evaluated comprehensively at Week 8.

- Effective
- Not effective
- Indeterminate (the reason should be recorded.)

The assessment criteria shall be as follows:

Table 2. Assessment criteria for [anaerobic infection] / [infectious enterocolitis (including pseudomembranous colitis)]

Assessment	Definition
Effective	Clinical symptoms accompanying the infection observed at the initiation of treatment with this drug has improved at the time of assessment, and treatment with other antibacterial drugs after the time of assessment is determined not necessary.
Not effective	"Effective" criteria are not met.
Indeterminate	Clinical response is difficult to evaluate.

Table 3. Assessment criteria for [amebic dysentery]

Assessment	Definition
Effective	Clinical symptoms accompanying the infection observed at the initiation of treatment with this drug has improved at the time of assessment, and treatment with other antibacterial drugs other than antiamebic agents (paromomycin, etc.) after the time of assessment is determined not necessary.
Not effective	"Effective" criteria are not met.
Indeterminate	Clinical response is difficult to evaluate.

Any clinically problematic finding compared to the initiation of treatment should be recorded in details in the AE column.

(2) Rationale for clinical response assessment

The rationale for the clinical response assessment ("Effective" or "Not effective"), on the disease for which this drug is used, should be recorded.

[Anaerobic infection]

General clinical findings, body temperature, WBC count, CRP level, imaging, and others

[Infectious enterocolitis (including pseudomembranous colitis)]

General clinical findings, Clostridium difficile TOXIN test, frequency of diarrhea, body temperature, abdominal pain, and others

[Amebic dysentery]

General clinical findings, ameba test, frequency of diarrhea, body temperature, abdominal pain, and others

(3) Microbiological response assessment

Microbiological response at the completion of observation period compared to prior to the initiation of treatment with this drug should be assessed, and the results should be recorded.

Table 4. Assessment criteria for microbiological response

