7.3.7. Adverse events

After confirming the occurrence of AEs from the initiation of treatment with this drug to the completion date of observation period, the following information will be recorded. Upon occurrence of any AE, the investigator should take appropriate measures, and promptly report to Pfizer Japan Inc. (hereinafter "Sponsor"), and if causal relationship with this drug cannot be ruled out, the investigator should follow up the event until the AE or its sequelae are resolved or stabilized at the level acceptable to the investigator and Sponsor.

Moreover, a study should be separately conducted in detail on patients in whom a serious adverse reaction, or an adverse reaction not described in the package insert occurred if it is determined necessary by Sponsor.

[1] Presence/absence of AE

[2] Name of AE

[3] Presence/absence of AE concerning central nervous system disorder

[4] Date of occurrence

[5] Intervention

[6] Seriousness

[7] Outcome

[8] Causal relationship

[If the AE is associated with abnormal change in laboratory values, i.e., clinical laboratory tests, the following information should also be recorded.]

[1] Laboratory parameter

[2] Site reference value

[3] Unit

[4] Date measured

[5] Results

Detailed study on adverse reactions concerning central nervous system disorder

Completion of detailed CRF should be separately requested on central nervous system disorder that occurred in patients subject to this study if it is determined necessary by Sponsor.

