7.6. Data management

7.6.1. Data collection method

The data for this study will be collected using a specific CRF provided by Sponsor. The investigator will complete the CRFs promptly after the completion of observation period and submit them to the Sponsor.

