9.2. Reporting period

For each patient, the safety event reporting period begins at the time of the patient's first dose of this drug, and lasts through the end of the observation period of the study, which must include at least 28 calendar days following the last administration of a drug under study; a report must be submitted to Pfizer Safety (or its designated representative) for any of the types of safety events listed in the table above occurring during this period. If a patient was administered a drug under study on the last day of the observation period, then the reporting period should be extended for 28 calendar days following the end of observation.

If the investigator becomes aware of a SAE occurring at any time after completion of the study and s/he considers the SAE to be related to this drug, the SAE also must be reported to Pfizer Safety.

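### Protocol 7.2.6 and 7.3.7 stop adverse-event recording at the last dose (or Day 56) while 9.2 runs 28 days longer, so late non-serious events fall under conflicting rules and the SAP's table of later reactions has no end day

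*SAP*

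**What the plan says.** **Observation and recording.** Protocol 7.2.6 states: "The observation period shall start on the day the treatment with this drug begins and end on the day the treatment is completed", with a cut-off at Day 56 for longer treatment. Protocol 7.3.7 ties adverse-event recording to the same date: "After confirming the occurrence of AEs from the initiation of treatment with this drug to the completion date of observation period". Protocol 7.6.1 adds: "The investigator will complete the CRFs promptly after the completion of observation period and submit them to the Sponsor". Treatment past Week 8 is foreseen in 7.3.6: "If this drug is administered continuously for more than 8 weeks, the clinical response should be evaluated comprehensively at Week 8".

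**Reporting.** Protocol 9.2 runs reporting through the end of the observation period, "which must include at least 28 calendar days following the last administration of a drug under study". For a patient dosed on the last observation day, "then the reporting period should be extended for 28 calendar days following the end of observation". Reports are due "for any of the types of safety events listed in the table above occurring during this period". The table meant is the one in 9.1. It sends serious events to both the CRF and the 24-hour NIS AE Report Form, and sends all non-serious events to the CRF and none to the form. Section 9 treats the form as part of the CRF.

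**Analysis.** SAP 8.2.3 says safety analysis is "primarily based on the data collected during the observation period that is from the start of Anaemetro administration to the end of Anaemetro administration". SAP 8.2.3.1 adds one table, by SOC and PT, of the number of patients whose adverse reactions began inside or outside the observation period. The listings in SAP section 9 are not restricted by window.

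**The concern.** One term, the observation period, is given two end dates about four weeks apart. Which one a site follows decides whether a non-serious event starting after the last dose is written down at all.

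The study is meant to show whether the kinds and frequency of reactions resemble those in Study A6831005 (Protocol 7.5.2, SAP 2.1), and it feeds the re-examination application. On-treatment incidence is a legitimate quantity, but it can only equal or fall below incidence through 28 days after the last dose. If sites send in late serious events reliably and late non-serious ones patchily, the outside column mixes full and partial ascertainment, and a reader who takes it at face value is misled about both frequency and seriousness.

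**Working it through.** **1. The plan's own figure.** Inputs from Protocol 7.5: 100 patients, true incidence 3%. Chance of at least one case = 1 − (1 − 0.03)^100 = 95.2%, which agrees with the stated 95%. That figure is not in dispute.

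**2. End day under each rule**, for last dose day L:

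| L | 7.2.6 and 7.3.7: min(L, 56) | 9.2 first sentence: L + 28 (minimum) | 9.2 extension: min(L, 56) + 28 |
|---|---|---|---|
| 7 | 7 | 35 | 35 |
| 14 | 14 | 42 | 42 |
| 56 | 56 | 84 | 84 |
| 70 | 56 | 98 | 84 |

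Under 7.2.6, any patient who finishes by Day 56 is dosed on the last observation day. The 9.2 extension therefore applies to all such patients, and the gap is always 28 days. Beyond Day 56 the two 9.2 rules part company: 98 − 84 = 14 days for L = 70. For uninterrupted courses of 7 and 14 days, the post-dose days make up 28/35 = 80% and 28/42 = 67% of the 9.2 window. These are shares of time, not of events.

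**3. Which late events are collected.**
- Serious: 9.1 and 9.2 require the NIS AE Report Form, and section 9 makes it part of the CRF. The route is clear.
- Non-serious, pointing towards collection: the 9.1 table (all on the CRF), 9.2 (every type in that table), and 9.3 (a 24-hour report when causality is unknown).
- Non-serious, pointing away: the 7.3.7 window, CRF completion under 7.6.1 soon after observation ends, and the 9.1 entry that no non-serious event goes on the form.

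**4. What the SAP reports after the last dose.** The table in 8.2.3.1 covers reactions only and gives counts only. It sets no end day for the outside column. Because it classifies each reaction, one patient may be in both columns, so the columns cannot be added. No proportion through the 9.2 window is planned for reactions, serious reactions, adverse events or safety specification items.

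**5. Calendar.** Protocol 7.2.4 ends registration in March 2017 and the investigation in May 2017. Take 31 March 2017 as Day 1. Day 34 is 3 May, and 28 days later is 31 May. Day 56 is 25 May, and 28 days later is 22 June. A late starter treated beyond Day 34 would therefore have a 28-day window that outlasts the investigation period.

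**6. Illustration only.** Let f be the share of a 3% reaction that starts after the last dose. The documents give no value for f, so every value here is an assumption. The chance of at least one on-treatment case is 1 − (1 − 0.03(1 − f))^100:
- f = 0: 95.2%
- f = 10%: 93.5%
- f = 20%: 91.2%
- f = 30%: 88.0%
- f = 50%: 77.9%

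Late cases that were collected would still appear in the inside/outside table and the listings.

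**The case against.** The strongest reply is that the windows serve different ends: 7.3.7 governs study recording, and 9.2 governs reports to the sponsor's safety unit. For courses up to Day 56, both 9.2 rules give one clear end day. The SAP already tabulates late reactions in a set with a known denominator, so counts convert to percentages, and with about 100 patients a reader can inspect late cases one by one in the listings. The study is not confirmatory and has no decision rules.

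Much of this stands, but two things remain. The first sentence of 9.2 speaks of the observation period itself, so it contradicts 7.2.6 directly. And neither percentages nor listings help with events that were never recorded.

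A reader might go further, in ways the documents do not support:
- *That the SAP conceals the on-treatment basis of its rates.* It does not. The sentence at the head of 8.2.3 states the window and governs the subsections under it.
- *That the SAP analyses events to Day 70 when the last dose is on Day 70.* The wording of 8.2.3 omits the cut-off, but SAP 2.1 defines the observation period with Day 56, and 8.2.3 uses that term. It is a point to tidy, not a separate window.
- *That the safety rates are too low by a known amount, or not comparable with Study A6831005.* Neither the late-onset share nor that study's adverse-event window is given.
- *That 28-day proportions for all events should simply be added.* If non-serious collection was patchy, those proportions would carry the same mixed ascertainment.

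**Conclusion.** The contradiction is real and sits in the Protocol. It is 28 days for every course ending by Day 56, with a further 14-day disagreement inside 9.2 for a last dose on Day 70. It follows from the text that non-serious events after the last dose are under conflicting rules. That late data are in fact incomplete and weighted to serious events is a possibility that depends on what sites did. The SAP's on-treatment rates are openly defined and can stay. Its weakness is narrower: the only table of later reactions has no end day, no proportions and no once-per-patient total. The size of any under-count cannot be determined from the documents, and the detection figures in step 6 rest wholly on assumed shares. This should be fixed because it changes which late events are captured and what the safety rates can support.

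**What to change.** 1. Reconcile Protocol 7.2.6, 7.3.7, 7.6.1 and 9.2 with SAP 8.2.3, including how Day 56 and the 28 days apply to treatment beyond 8 weeks. The choice of window is the sponsor's.
2. In the SAP, keep the on-treatment rates and close the outside column at the reconciled end day.
3. Add numbers and proportions of patients with onset through that day, each patient counted once, for serious reactions and serious adverse events. Do the same for all reactions, all adverse events and the safety specification items only if non-serious post-dose events were collected systematically.
4. If they were not, state this as a limitation and say that the outside counts are not complete.

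Cost: a few tables and changes of wording. The last SAP revision describes the database release as in preparation, so collection may already be closed; the work is then limited to tables for what was collected and the limitation statement. If collection is still open, CRF closure may come somewhat later.

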8.2.3.1. Adverse Reactions

- **Adverse reactions**

The number and proportion of patients with adverse reactions will be tabulated by SOC and PT.

- **Serious adverse reactions**

The number and proportion of patients with serious adverse reactions will be tabulated by SOC and PT.

- **Details of adverse reactions**

The number and proportion of patients with adverse reactions will be tabulated by SOC and PT for each of the following items.

- Seriousness [serious, non-serious]
- Expected/unexpected [Expected, unexpected]
- Intervention [discontinuation, temporarily discontinued or dose reduced]
- Outcome [not recovered, recovered with sequela, recovering, resolved/recovered, unknown]

In addition, the number and proportion of patients with adverse reaction that meets all of the following items will be tabulated by SOC and PT:

- The seriousness was considered “non-serious”;
- The intervention was “discontinuation”, “temporarily discontinued”, or “dose reduced”
- The outcome was “not recovered” or “recovered with sequela”.

If the same adverse reaction (the same PT) occurs more than once in the same patient, it will be handled as follows in the tabulation of the number of patients with events:

- Seriousness: If both serious and non-serious events are reported, “serious” will be adopted.
- Expected/unexpected: If both expected and unexpected events are reported, “expected” will be adopted.
- Number of days to onset: The number of days to the first event will be adopted
- Intervention: If multiple types of action are reported, one of discontinuation, temporarily discontinued or dose reduced, or other (none, dose increased), in descending order of precedence, will be adopted.
- Outcome: The outcome of the last occurring event will be used.

- **Safety specification items**

The number and proportion of patients with the following safety specification items will be tabulated.

- Central nervous system disorder
- Peripheral nerve disorders
- Aseptic meningitis
- Toxic epidermal necrolysis, oculomucocutaneous syndrome
- Acute pancreatitis

- Leukopenia, neutropenia
- Carcinogenicity

In addition, the number and proportion of patients who experienced each safety specification item will be tabulated by intervention and outcome, by SOC and PT.

In order to explore factors common to those who experienced the safety specification items, listings of patient background and concomitant medications for patients who experienced the most frequent safety specification items will be tabulated.

- **Time to adverse reaction**

The number of patients who experienced an adverse reaction will be tabulated by time to first development (≤ 3 days, ≥ 4 to ≤ 10 days, > 10 days), by SOC and PT.

- **Adverse reactions by patients of included/excluded in the safety analysis set**

In completed patients, the listing of adverse reactions in patients excluded from the safety analysis set will be prepared. In addition, the number of patients with events will be tabulated by SOC and PT.

- **Adverse reactions that developed within and outside the observation period**

Using the safety analysis set, the number of patients with adverse reactions will be tabulated by whether each reaction developed within or outside the observation period, by SOC and PT.

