6. RESEARCH QUESTION AND OBJECTIVES

This study will be conducted to investigate the safety and effectiveness of this drug in daily clinical practice. Additionally, it is intended to assess the following:

- Adverse reactions unexpected from precautions, and
- Occurrence of adverse reactions under actual clinical settings

"Central nervous system disorder" also will be confirmed for the tendency of adverse reactions under actual clinical settings.

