9.1. Requirements

The table below summarizes the requirements for recording safety events on the CRF and for reporting safety events on the NIS AE Report Form to Pfizer Safety. These requirements are delineated for three types of events: (1) serious adverse events (SAEs); (2) non-serious AEs (as applicable); and (3) scenarios involving drug exposure, including exposure during pregnancy (EDP), exposure during breast feeding, medication error, overdose, misuse, extravasation, lack of efficacy, and occupational exposure. These events are defined in the section "Definitions of safety events".

Safety event	Recorded on the CRF	Reported on the NIS AE Report Form to Pfizer Safety within 24 hours of awareness
SAE	All	All
Non-serious AE	All	None
Scenarios involving exposure to this drug, including EDP, exposure during breast feeding, medication error, overdose, misuse, extravasation, lack of efficacy, and occupational exposure	All (regardless of whether associated with an AE), except occupational exposure	All (regardless of whether associated with an AE)

For each AE, the investigator must pursue and obtain information adequate both to determine the outcome of the AE and to assess whether it meets the criteria for classification as a SAE (see section "Serious adverse events" below)

Safety events must be reported to Pfizer within 24 hours of awareness of the event by the investigator as described in the table above **regardless of whether the event is determined by the investigator to be related to a drug under study**. In particular, if the SAE is fatal or life-threatening, notification to Pfizer must be made immediately, irrespective of the extent of available event information. This timeframe also applies to additional new (follow-up) information on previously forwarded safety event reports. In the rare situation that the investigator does not become immediately aware of the occurrence of a safety event, the investigator must report the event within 24 hours after learning of it and document the time of his/her first awareness of the events.

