9.5. Single reference safety document

A Single Reference Safety Document (SRSD) refers to a document that contains the information on the known safety profile. The package insert of this drug will be the SRSD in this study. Pfizer Japan Inc. will evaluate the safety information reported by the investigator during the study period using the SRSD.

The investigator will also prescribe the drug and give the drug administration guidance based on the SRSD.

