8.2.3.4. Subgroup Analysis

The number and proportion of patients who experienced at least one adverse reaction will be tabulated for each factor specified in Section 5.4. To evaluate the relationship between patient background factors and the development of adverse reactions, the analysis based on risk ratio and risk difference specified in Section 8.1.3 will be performed. For subgroups with

risk ratio ≥ 2 or ≤ 0.5 , the number and proportion of patients who experienced adverse reaction will be summarized for each factors, using SOCs and PTs. It should be noted that if adverse reactions developed in less than a total of 10 patients, the risk ratio and risk difference will not be calculated, although the proportion will be presented for each factors.

The number and proportion of patients who experienced adverse reaction will be summarized by maximum number of daily doses, based on SOCs and PTs. Similarly, the number and proportion of patients who experienced serious adverse reaction will be summarized by maximum number of daily doses.

Listing of adverse reactions that developed in contraindicated patients will be tabulated. In addition, the number and proportion of those contraindicated patients who experienced adverse reactions will be tabulated by SOC and PT, as necessary.

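### When one patient has the same reaction term as both expected and unexpected, the SAP counts it as expected, against the stated objective of assessing unexpected reactions

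*SAP*

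**What the plan says.** SAP 8.2.3.1 plans the number and proportion of patients with adverse reactions by SOC and PT, split in turn by seriousness, expectedness, intervention and outcome. When a patient has the same PT more than once, a list of rules decides which value is counted:

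- Seriousness: "If both serious and non-serious events are reported, “serious” will be adopted".
- Expectedness: "If both expected and unexpected events are reported, “expected” will be adopted".
- Days to onset: the first event counts.
- Intervention: discontinuation ranks first, then interruption or dose reduction, then other actions, "in descending order of precedence, will be adopted".
- Outcome: "The outcome of the last occurring event will be used".

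Protocol 6 lists two bulleted aims under the general safety and effectiveness objective. The first is "Adverse reactions unexpected from precautions, and" the second is the occurrence of adverse reactions in actual practice. SAP 2.2 repeats both. The reference for what is already known is set in Protocol 9.5: "The package insert of this drug will be the SRSD in this study".

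**The concern.** The expectedness rule keeps the class that is not the subject of the objective. A patient with one expected and one unexpected episode of the same PT disappears from the unexpected column. The reverse error cannot occur, so any distortion goes one way.

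The rule also runs opposite to its neighbours for seriousness and intervention, which retain the more notable value. The list is not worst-case throughout, since outcome takes the last event and onset the first. The main ground is therefore the objective, not symmetry.

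This is the only tabulation whose SAP text names expectedness, so it is the planned summary for that aim. In a study of about 100 patients, a single patient can decide whether a PT appears in the unexpected column at all.

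**Working it through.** **Inputs.** Planned safety sample 100 (Protocol 7.5.1). Detection target 95% for a reaction with 3% true incidence (Protocol 7.5.2). Observation at most 56 days (Protocol 7.2.6). Threshold of 10 patients with adverse reactions, below which risk ratios and differences are not calculated (SAP 8.2.3.4: "if adverse reactions developed in less than a total of 10 patients"). The documents do not say how often a PT repeats within a patient or how often the repeats are mixed.

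**1. The plan's own figure.** 1 − 0.97^100 = 0.952, so the stated 95% reproduces. The smallest sufficient sample is ln 0.05 / ln 0.97 = 98.4, rounded up to 99. This figure concerns seeing the reaction at all. The collapsing rule does not alter it, nor the total count per PT.

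**2. Effect per affected patient.** Take a PT that is unexpected in one patient only, who also has an expected episode of it. Exact (Clopper-Pearson) intervals for the unexpected cell:

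- Current rule: 0/100 = 0%, upper limit 1 − 0.025^(1/100) = 3.6%.
- Reversed rule: 1/100 = 1.0%, interval 0.03% to 5.4%.

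The SAP specifies only number and proportion for this table. The intervals are given here to show how little information separates the two cells.

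**3. How many patients (assumed inputs).** Let A be the patients with any adverse reaction, r the share of them who repeat a PT, and m the share of those repeats that are mixed. A = 10 is borrowed from the SAP threshold and is not a forecast; r = 5% to 20% and m = 1% to 20% are assumptions.

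- Expected number affected = A × r × m: 10 × 0.05 × 0.01 = 0.005, up to 10 × 0.20 × 0.20 = 0.4.
- Chance of at least one = 1 − (1 − r × m)^10: 1 − 0.9995^10 = 0.5%, up to 1 − 0.96^10 = 33.5%.

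**4. Dependence on the mixed share for one PT.** Suppose 3% of patients have a given PT as unexpected at least once, and a share s of those also have it as expected (s is assumed). The current rule leaves 100 × 0.03 × (1 − s) expected patients in the unexpected column. The chance of at least one there is 1 − [1 − 0.03(1 − s)]^100.

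| s | Expected count, current rule | Chance of at least one, current rule |
|---|---|---|
| 0% | 3.0 | 95.2% |
| 10% | 2.7 | 93.5% |
| 25% | 2.25 | 89.7% |
| 50% | 1.5 | 77.9% |
| 100% | 0 | 0% |

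Under the reversed rule the figures are 3.0 and 95.2% in every row. With no mixed repeats the two rules agree.

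**The case against.** The strongest reply is that little can be lost. A mixed case means that at least one episode of the PT was classed as expected, so the package insert already covers that PT in some form. A PT that is only ever unexpected in a patient stays in the unexpected column. Expectedness is not among the adverse-event items the investigator records (Protocol 7.3.7), and the sponsor evaluates reports against one reference document, so mixed classes should be rare. A change to the insert during the study could produce them, and then keeping the expected class might be defensible.

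Other routes also work on the reactions themselves and not on the collapsed table. Protocol 9.1 states "Safety events must be reported to Pfizer within 24 hours of awareness of the event by the investigator" for the event types in its table. Protocol 7.3.7 allows a separate detailed study of reactions absent from the insert, and Protocol 15 sets out actions when a serious unknown reaction is suggested. SAP 9 plans listings of adverse reactions.

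Most of this stands, and it limits the size. It does not supply a reason for the rule. The SAP does not mention a change of insert. Non-serious reactions are generally outside the 24-hour route. The detailed study is at the sponsor's discretion, and SAP 9 does not say that its listings show expectedness. Nothing here makes the chosen precedence serve the objective better than its opposite.

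**Conclusion.** The point holds as a reporting weakness of small reach. The rule can only under-count patients with an unexpected reaction, in the one table whose text addresses that aim, and it is given without a reason. The loss is one patient in the unexpected column per mixed repeat of a PT.

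How often this happens cannot be computed from the documents. The range of 0.005 to 0.4 patients rests entirely on the assumed A, r and m. Rarity is plausible: the sample is about 100, observation is short, there is one reference document, and the SAP's amendment record cites limited numbers of patients with adverse events when dropping analyses. Overall incidence, the design's detection probability and the reporting duties are untouched. The change should be made, but the study does not depend on it.

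**What to change.** In the expectedness bullet of SAP 8.2.3.1, replace the adopted value with *unexpected*. In the listing of patients with adverse reactions (SAP 9), show seriousness and expectedness for each episode.

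The cost is one word and at most two listing columns; SAP 9 does not specify columns, so they may already be intended. The unexpected count may rise slightly.

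One artefact should be acknowledged. A patient with a serious expected episode and a non-serious unexpected one would be counted as serious and as unexpected, although no single episode is both. The current rule has the mirror-image problem, so the change is no better or worse on that point. The SAP text plans no cross-table of the two attributes, and the per-episode listing resolves either case.
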